## **6.0 Number of Subjects**

Total enrollment number is 160. We plan to acquire full data sets from 144 individuals (24/group) to allow for a 10% rate of data loss due to motion artifacts in the MRI scanner. This will require 160 individuals to be invited to the consent/screening visit.

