*Participants.* We plan to acquire full data sets from 144 individuals (24/group) to allow for a 10% rate of data loss due to motion artifacts in the MRI scanner. This will require 160 individuals to be invited the Consent/Screening Visit (V1)(see Targeted Enrollment Plan, Inclusion of Women & Minorities). This is based on a 66% eligibility rate from V1 (screening) to V2, followed by a 90% retention rate from V2 to V3. These enrollment and retention rates are based on prior studies by [name] in cocaine users which have used the MUSC Intensive Outpatient Program as a recruitment source (R01DA036617, R21DA041610). Treatment-seeking cocaine-dependent men and women, 18- 65 years old will be enrolled through the MUSC intensive outpatient substance abuse treatment program (see below) or their own initiated contact from study recruitment advertisements and randomized to receive either real or sham cTBS (stratified by gender). Randomization is appropriate for this sample [14] and therefore used to assign participants to experimental arms.

*MUSC Intensive Outpatient Treatment Program.* (More details of this program are found in Resources). Briefly, the program consists of 20 total treatment days (4 hours/day), spread across 4-5 weeks. Participants attend daily individual and group therapy sessions with staff certified in Cognitive Behavioral Therapy, contingency management, motivational interviewing and other established addiction treatment practices. Approximately 8-10 cocaine dependent individuals enroll in the Intensive Outpatient Program each month (60% male, 84% between the ages of 21-45, 10% of whom are court-ordered). The retention

rate for cocaine dependent individuals is 72% for the 4-week outpatient program, with 60% attending 1 month and 44% attending 2-month Accountability/Continuity visits. Participants will not be exclusively recruited from this treatment program – they will also be recruited from the community as we intend to enroll any adult that meets inclusion criteria.

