Power analyses for study Aim 1—effects of cTBS on corticostriatal rsFC and cue-reactivity—were based on pilot data from a sham-controlled crossover study in which interleaved TMS/MRI was used to assess functional connectivity in cocaine users immediately before and after they received real or sham mPFC cTBS (see Significance). In these preliminary data in 12 cocaine users, real cTBS resulted in a larger effect on BOLD signal in the medial prefrontal cortex (eigenvalues real cTBS  $0.62 \pm 0.24$  vs. sham cTBS  $0.33 \pm 0.44$ ; Cohen's  $d=0.72$ ). Subjects will be assessed at 2 time points (m) with an anticipated interclass correlation coefficient (ICC) of 0.8 for the within subjects measures. The design effect accounts for multiple correlated observations within each subject, is estimated to be 1.8 (DE=  $[1+(2-1)0.8]$ );[15]. To allow for a 10% rate of data loss due to motion artifacts in the MRI scanner we have planned to enroll 160 individuals.

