## 12.0 Data Management

Prior to formal statistical analysis, summary statistics for all variables will be obtained and spaghetti plots will be generated. All behavioral outcome measures will be based on standardized composite scores from

the literature. We will also use data reduction techniques (such as factor analysis or principle component analysis) to confirm the applicability of the composite scores in our population. In the interests of eventually translating these mechanistic data to a larger clinical trial, we will perform a preliminary Intent-to-Treat analysis on each of the 6 groups to estimate effect sizes for a subsequent power analysis. Analyses will be performed for each phase separately. Image pre-processing will be conducted with FSL v. 5.0: (FMRIB Analysis Group, Oxford, UK) [33] realignment to the first volume, smoothing with an anisotropic 8-mm Gaussian kernel, high-pass filtering, resampling to 2-mm isotropic voxels, and stereotactic registration to the Montreal Neurological Institute 152-subject average template. Subjects with >3 mm movement (total mean frame displacement across the entire task) will be excluded from analysis.

**Specific Aim 1 (cTBS):** Evaluate mPFC cTBS as a tool to modulate corticostriatal rsFC and drug cue-reactivity in treatment-seeking cocaine users.

**Rationale:** Drug cues reliably activate the mPFC & ventral striatum in multiple classes of substance users, including cocaine users. Through an LTD-like form of TBS it is possible to decrease activity in the mPFC and the ventral striatum in chronic cocaine users and alcohol users [9]. **Primary dependent measure:** Change in cue-evoked brain activity and rsFC in corticostriatal circuitry after real but not sham cTBS. **Hypothesis:** LTD-like cTBS to the MPFC of individuals with cocaine use disorder will decrease cocaine cue-reactivity BOLD response in corticostriatal nodes (i.e. mPFC, ventral striatum) and strengthen rsFC between these key nodes.

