**RIGOR AND REPRODUCIBILITY: Strategies to Ensure a Robust and Unbiased Approach:** The proposed study will achieve robust and unbiased results via explicit inclusion/exclusion criteria; randomization of treatment condition order and examination of order effects; sham control; double blinding; sophisticated compliance monitoring at MUSC; use of validated MRI, laboratory, and interview/self-report measures; explicit hypotheses; power estimates; planned handling of attrition and missing data; and careful consideration of potential confounds. Methodology is reported in a detailed and fully transparent manner to support replication

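### A missing-data plan is claimed but not given; the implied analysis is complete-case with whole-subject motion exclusion, and adjustment for the pre-cTBS scans is left unspecified

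*Combined protocol and SAP*

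**What the plan says.** Section 12.0 (Rigor and Reproducibility) names "planned handling of attrition and missing data" as one of the features that make the results robust. The only related rule at the analysis stage is earlier in Section 12.0: "Subjects with >3 mm movement (total mean frame displacement across the entire task) will be excluded from analysis". It does not say whether one bad session removes the participant's other sessions, or whether the resting-state data go as well.

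Loss is expected. Section 10.0 (Participants) assumes a 66% eligibility rate from V1 to V2, "followed by a 90% retention rate from V2 to V3". The power paragraph of Section 10.0 adds: "To allow for a 10% rate of data loss due to motion artifacts in the MRI scanner we have planned to enroll 160 individuals". Section 1.0 places randomisation after V2, so loss between V2 and V3 falls after randomisation.

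The primary dependent measure in Section 12.0 is the change in cue-evoked activity and resting-state connectivity. The methods paragraph says only that percent signal change will be compared between real and sham, and names no model. The visit procedures in Section 10.0 give three MRIs (MRI 1 at V2; MRI 2 and MRI 3 at V3, before and after cTBS), while the overview and the power paragraph count two time points. Section 12.0 also mentions a preliminary intent-to-treat analysis on six groups, meant for planning a later trial.

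The Rigor sentence further claims "randomization of treatment condition order and examination of order effects".

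**The concern.** A reader who looks for the claimed plan finds no analysis set, no model for incomplete scan series, no missingness assumption, no sensitivity analysis, and no rule for someone who misses V3 or has one unusable session. Section 14.0 allows withdrawal but does not say how the data already collected are used. A change measure, a target of full data sets and subject-level exclusion together point to a complete-case comparison.

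Three things are at stake. Usable scans may be discarded. The comparison may be made on a subset whose pre-cTBS response differs by arm. And the baseline scan, the exclusion unit and the model could all be chosen after the data are seen.

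**Working it through.** **The plan's own figures.** 144 / (1 − 0.10) = 160 reproduces the enrolment number, so the 10% motion loss is meant per subject. That step leaves out the 10% lost from V2 to V3. Taking both, 1 − 0.90 × 0.90 = 0.19. If 160 were randomised, 160 × 0.81 = 129.6 full data sets would remain.

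**Inputs for what follows.** The ICC of 0.8 is from the power paragraph. Assumptions of this review: equal correlation of 0.8 between any two scans, unit variance, motion failures independent across scans, and 1:1 allocation.

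**Residual variance of the arm contrast**
- Change score, MRI 3 − MRI 2: 2(1 − 0.8) = 0.40
- MRI 3 adjusted for MRI 2: 1 − 0.8² = 0.36
- MRI 3 adjusted for MRI 1 and MRI 2: 1 − 2(0.64)/1.8 = 0.289
- MRI 3 with no usable pre-cTBS scan: 1.00

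Against the change score, adjusting for MRI 2 cuts variance by 10% (0.36/0.40 = 0.90). Adjusting for both cuts it by 28% (0.289/0.40 = 0.72).

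**What whole-subject exclusion costs.** Information per randomised participant is the sum of (share with that scan pattern) / (residual variance).

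*Three scans.* A 10% subject loss means a per-scan failure rate p = 1 − 0.9^(1/3) = 0.0345.
- Complete cases only: 0.900/0.289 = 3.115
- Add participants with MRI 3 and one pre-cTBS scan: 2p(1 − p)² = 0.0643; 0.0643/0.36 = 0.179
- Add participants with MRI 3 alone: p²(1 − p) = 0.001; 0.001/1 = 0.001
- Total 3.295; ratio 3.295/3.115 = 1.06

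*Two scans.* p = 1 − 0.9^(1/2) = 0.0513.
- Complete cases only: 0.900/0.36 = 2.500
- Add participants with MRI 3 alone: p(1 − p) = 0.0487; 0.0487/1 = 0.049
- Total 2.549; ratio 1.02

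Participants lost between V2 and V3 have no MRI 3. Keeping their MRI 1 adds nothing to the arm contrast.

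**Bias, as an illustration with invented inputs.** Suppose no true effect, 16% loss in the active arm rising with MRI 2 (logit slope 1 per SD), and 10% random loss in sham. By simulation, the retained active arm has an MRI 2 mean about 0.14 SD too low. The unadjusted post-scan difference is then 0.8 × (−0.14) = −0.11 SD, and the change-score difference is (0.8 − 1) × (−0.14) = +0.03 SD. A regression of MRI 3 on arm and the pre-cTBS scans gives 0.00, even when fitted to complete cases only.

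**The case against.** A reader might infer that the plan prescribes a complete-case analysis in which one bad scan forfeits all the others. The text does not say so. No primary model is named, and the motion rule is silent on sessions. Complete-case is the default reading only.

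A reader might also infer a large loss of precision. A gain of 18% from using all scans arises only if 10% motion loss applies to each scan (0.9³ = 73% of participants kept). That conflicts with 144/0.9 = 160.

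Nor do the documents support a stated amount of bias. They give no loss by arm. The −0.11 SD above belongs to an unadjusted post-scan comparison, while the plan's measure is change, where the same scenario gives +0.03 SD. Since complete-case regression also removes it, the example argues for baseline adjustment and not for keeping incomplete participants.

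Loss between V2 and V3 also comes before any stimulation, under blinding and without study medication, so treatment itself cannot cause it. Only loss on the day after cTBS could respond to treatment. This stands, and is why the two kinds of loss should be reported apart.

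The intent-to-treat sentence does bear on who is analysed. But it is preliminary, refers to six groups in a two-arm trial, and says nothing about missing scans, so it does not fill the gap.

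**Conclusion.** The concern holds in a limited form. The claimed handling of attrition and missing data appears nowhere, and the one stated rule acts on the subject where the design has three sessions. The stated rates imply about 19% of those at V2 without a full data set, all lost after randomisation, with only the motion part covered by the enrolment figure.

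Discarding single bad scans costs about 2% (two scans) to 6% (three scans) of information. The larger gain is from adjusting for the pre-cTBS scans, which takes residual variance from 0.40 to 0.36 or 0.29. These sizes rest on equal correlation of 0.8, independent motion failures and 10% motion loss per subject. Adjustment also protects against loss that depends on the observed pre-cTBS response; how much bias it would prevent is unknown.

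The treatment-order phrase is a separate wording matter. Each participant receives one condition, so there is no treatment order to randomise. The counterbalanced task runs in Section 10.0 are not treatment order.

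**What to change.** - **Section 12.0, pre-processing:** apply the motion rule to the run or scan instead of the subject, and say whether it also governs the resting-state data.
- **Section 12.0, methods and analysis:** compare real with sham using one likelihood-based repeated-measures model over MRI 1–3, with arm-by-scan terms and pre-cTBS means set equal across arms. Include every randomised participant with at least one usable scan. This also settles which scans serve as baseline, and should be reconciled with the two time points in Section 10.0.
- **Reporting:** give losses by arm and reason, separating loss before cTBS from loss after it.
- **Sensitivity:** add one shift (delta) analysis for missing MRI 3.
- **Rigor and Reproducibility:** point to these rules and delete the treatment-order claim.

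The cost is analysis-plan wording and a standard mixed model, with no new data or participants. The downside is that the model assumes data are missing at random given the observed scans; the shift analysis tests how far the result depends on that.

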### 13.0 Provisions to Monitor the Data to Ensure the Safety of Subjects

**Sources of Material:** A total of 144 individuals will be enrolled in the current project. The behavioral assessments, as well as biological data (laboratory and neuroimaging results) will be collected only after

obtaining informed consent, and for research purposes only. These records will be kept by [name] in password protected confidential electronic files with restricted access.

**Confidentiality Procedures:** As the PI, [name] will assure all procedures protecting study data designed to guard subject confidentiality conform to the MUSC Research Protection Program requirements. Additionally, the MUSC IRB must approve all procedures and safety precautions before the study can begin. All data (clinical evaluations, MRI data, TMS data) will be stored securely in locked offices or laboratories accessible only by study staff. Further, all information that could potentially identify a subject directly is removed from all study data. This includes electronic and paper assessments, MR images, and biological samples. This will be replaced with a unique four-digit code. The key to linking the code to subject identity will be kept separately from study data, in a locked electronic file. Only study staff involved in clinical recruitment and assessment will have access to individually identifiable private information. All other study staff will only have access to the coded identifier.

#### **14.0 Withdrawal of Subjects**

Female participants who become pregnant during the study will be withdrawn from the study. Additionally, the Investigator has the right to withdraw a participant at any time.

#### **15.0 Risks to Subjects**

The main study procedures include brain stimulation, a medication trial, clinical evaluation, MRI, and completion of questionnaires. Although these procedures do carry minimal risk, the primary risks of the study are a) adverse effects of study medications, b) emotional distress, c) incidental findings, and d) loss of confidentiality. The primary risks are described below:

**1. Magnetic Resonance Imaging.** Because the MRI machine acts like a large magnet, it could move metallic objects in the MRI room during the examination, which could be harmful to the participant. To prevent such an event from happening; loose metal objects, like pocket knives or key chains, are not allowed in the MRI room. If a participant has a piece of metal in their body, such as a fragment in their eye, aneurysm clips, ear implants, spinal nerve stimulators, or a pacemaker, they will not be allowed into the MRI room and cannot have a MRI.

Having a MRI may be uncomfortable, particularly regarding feelings of claustrophobia and the loud banging noise during the scan. Participants will be asked to wear earplugs to avoid possible hearing impairment.

#### **2. Transcranial Magnetic Stimulation:**

- a. **Investigational Device Exemption:** Transcranial Magnetic Stimulation is an investigational device. The IRB at MUSC (in cooperation with the FDA) have determined repetitive TMS to be a non-significant risk intervention.
- b. **Potential Risks of TMS**
  - 1). **Potential risk of a seizure:** The major risk using repetitive TMS subjects is the possibility of inducing a seizure. We have now studied and given rTMS to more than several hundred subjects over past 15 years. None of these patients has developed a seizure. We will exclude patients with a prior history of seizures.
  - 2). **Potential for scalp discomfort and headaches:** Some people report mild discomfort when the magnetic pulses are applied over the scalp. A small number of people (~5%) report headache following TMS. However, the headaches are temporary and manageable with common over-the-counter pain remedies.
  - 3). **Potential hearing loss:** The discharge of the rTMS coil generates a high-energy click that may cause cochlear damage. Foam earplugs can protect against these changes and will be worn by the subjects and the researchers present during TMS sessions.

**3. Incidental Findings: Magnetic Resonance Imaging:** Some MRI scans can detect medical conditions, such as cancer, brain injury, and abnormal blood vessels; however, this functional MRI is carried out

purely for experimental purposes and we are not looking for brain disorders. Furthermore, the study researchers are not trained in diagnosing brain disorders; therefore, the researchers are not qualified to offer any medical opinions concerning the scan (good or bad). It is possible that the study researchers will notice something in a participant's scan that appears unusual and/or abnormal, if this occurs, the researchers will inform the participant of the finding and provide them with a copy of their scan, which they may take to a medical expert for further review and diagnosis. Being told about such a finding may cause anxiety as well as suggest the need for additional tests and financial costs. Any costs associated with clinical follow-up(s) are the participant's and/or the participant's insurance carrier's responsibility. Participants who do not wish to be informed of such findings will be advised to not participate in this study.

4. Breach of confidentiality: There is the potential risk of breach of confidentiality of clinical and laboratory information. [name] has experience as an investigator dealing with such sensitive information and has experience assuring that data is adequately protected. Safeguards to protect confidentiality include locked records and firewalls around password-protected electronic data, and all study data being coded, with the key linking the code with a participant's identity being kept on secure network storage as a password protected document. Similar safeguards are followed for storage and processing of MRI data. MRI data is stored on secure network storage maintained by MUSC, where the PI has dual appointment. The MRI scans are identified only by subject code, study code, and date of acquisition. Participants' initials will also be present on some questionnaires; however, the questionnaires containing the initials will be stored in a locked file cabinet.
5. Interview and psychiatric emergencies: Subjects may experience discomfort during the clinical interview and evaluations when discussing symptoms, life events, and social support. The Research Coordinator and Specialists will be experienced and skilled in interviewing subjects. Should the subject wish to stop or take a break, they will allow it. In addition, should the subject express any physical or psychological symptoms that are concerning or possibly represent an emergency, the study physician ([name]) or other approved study clinician will be contacted immediately to assess the subject and to determine the appropriate course of action. Possible situations where this would occur include but are not limited to thoughts of suicide, homicidal or violent thoughts, psychosis, or a change in the subject's physical status if they start feeling bad or complaining of new physical symptoms (such as chest pain, acute nausea, etc.). Importantly, the Research Coordinator/Specialist is not the only individual screening for such potential emergencies. These domains will be independently assessed by [name]/PA-C during the health and physical exam and any subsequent future clinical interview. Options for addressing such emergencies may include contacting the individual's mental health caregiver, referring for urgent evaluation and treatment, or emergent hospitalization.

#### ADEQUACY OF PROTECTION AGAINST RISKS

- a. *Recruitment and Informed Consent.* Participants will be recruited from the general community through media advertising (print and online sources). The IRB approved Informed Consent (IC) will be obtained prior to the initial assessment. The consent will be explained orally and in the written form, and will be documented by the signature of the participant on the IC. Consent will be obtained in a private interview room so that the participant may ask any questions to the research staff.
- b. *Protection against Risk.* Research staff will closely supervise participants throughout their enrollment in the study. Specific to the BAC assessment, if a participant's BAC is greater than 0.0 at any visit, the research staff will either a) ask the participant to remain in the laboratory until their BAC returns to

0.0, if they are driving, or b) work with the participant to ensure that they have alternative transportation home, including providing a taxi, if needed.

c. *Loss of confidentiality:* Paper-based information will be kept in on-site locked file cabinet(s) designated for study materials. Data collection instruments or forms containing participant names will be stored in separate secure locations from those instruments or forms containing subject identification (SID) numbers, and both will be stored separately from the master list linking the SID and names. Paper-based information will be accessible only to study personnel who need access to the information for study purposes. All electronic records will be stored on a password protected secure server with access limited only to study personnel who need access to the information for study purposes. All password protected hard-drive backups will be stored in the PI's offices in a secure location. The results of drug and BAC testing will be stored in the same manner as other data (i.e. in separate location from any information containing participant PHI). The results will not be reported to any authority (e.g. employer or law enforcement) nor will they be available to them upon request.

## **16.0 Potential Benefits to Subjects or Others**

Participants will not directly benefit from this study.

